10.2.5 Visit 5 (Day 1-Insertion Period 2)

1.	Obtain information on any changes in medical health and/or the use of concomitant medications
2.	Record any AEs, including those associated with changes in concomitant medication dosing and Device Deficiencies that are observed or reported
3.	Confirm subject compliance with no lens wear and confirm no use of artificial tears during the study as well as no use of rewetting drops on the day of study visit
4.	Assess monocular logMAR BCVA
5.	Assess biomicroscopy
6.	Administer randomized study lenses no earlier than 15 minutes after biomicroscopy, record time of insertion
8.	Verify Lens Fit approximately 15 minutes after insertion
0.	Note: if the fit of the control contact lens is not suitable the contact lens needs to be
	removed and the alternative base curve tried
9.	Conduct a spherical over-refraction and optimize the Rx as required (binocular
).	optimization)
10.	Assess monocular logMAR VA with lenses (with and without spherical over-
10.	refraction) (record VA with study lenses and without spherical over-refraction in
	EDC)
15.	Schedule Visit 6 to take place at Day 30 (+3). Instruct subjects on study compliance
	requirements. Inform subject to wear the lenses for 10 hours \pm 30 minutes on the
	visit day and not to use artificial tears during the study period or rewetting drops on
	day of visit. Instruct to use habitual lens care to care for their lenses daily

Effective Date: 07-Dec-2017

Version: 3.0; Most-Recent; Effective; CURRENT Document: TDOC-0053541

Status: Effective Page 41 of 59

10.2.6 Visit 6 (Day 30 Period 2 - Last Study Visit – Exit)

1.	Obtain information on any changes in medical health and/or the use of concomitant medications
2.	Record any AEs, including those associated with changes in concomitant medication dosing and device deficiencies that are observed or reported
3.	Confirm subject compliance with lens wear and confirm no use of artificial tears during the study as well as no use of rewetting drops on the day of study visit
4.	Assess subjective acceptance of study lenses
5.	Assess monocular logMAR VA with lenses (with and without spherical over-refraction) (record VA with study lenses and without spherical over-refraction in EDC)
9.	Assess Lens Fit
10.	Aseptic contact lens removal and storage in freezer of study lenses for ex vivo lipid uptake analysis ((total, individual, surface, bulk))
11.	Assess biomicroscopy
12.	Assess monocular BCVA with Manifest Refraction
13.	Exit subject from the study

Document: TDOC-0053541 **Version:** 3.0; Most-Recent; Effective; CURRENT

Status: Effective Page 42 of 59

10.3 Unscheduled Visits

Any visit that occurs between the regularly scheduled visits must be documented in the Unscheduled Visit pages of the electronic Case Report Form (eCRF).

If a subject needs a lens replacement, an unscheduled visit should be performed. Subjects will not restart the study period in the case of an unscheduled lens replacement.

During all unscheduled visits, the following procedures should be conducted:

1.	Obtain information on any changes in medical health and/or the use of concomitant medications
2.	Record any AEs, including those associated with changes in concomitant medication dosing and Device Deficiencies that are observed or reported
3.	Assess monocular logMAR VA with lenses (as needed)
4.	Assess monocular BCVA with Manifest Refraction
5.	Assess biomicroscopy

If the subject discontinues at the unscheduled visit, all the assessments listed for Visit 4/Visit 6 should be performed. The Exit Form should also be completed.

10.4 Screen Failures

Subjects who do not meet inclusion/exclusion criteria for study participation will be considered screen failures and must not be re-screened.

10.5 Discontinued Subjects

Discontinued subjects will include those who withdraw or are withdrawn from the study after randomization at Visit 3. Subjects may discontinue from the study at any time for any reason. Subjects may also be discontinued from the study at any time if, in the opinion of the Investigator, their continued participation poses a risk to their health. Discontinued subjects will not be replaced (ie, their subject numbers will not be re-assigned/re-used).

Should a subject exhibit any clinically relevant signs, symptoms, or other clinical observations that could possibly be associated with suspected sensitivity or intolerance to one of the study lenses, the Investigator must document those observations on an AE Form.

Document: TDOC-0053541 Version: 3.0; Most-Recent; Effective; CURRENT

Status: Effective Page 43 of 59

Any subject who exits early from the study should undergo all procedures outlined at Visit 4/Visit 6. Additionally, the Exit Form must be completed and the reason for discontinuation identified.

Finally, Investigators should assess each subject to ensure the safety of those who discontinue early, and, if necessary, advise them of any therapies and/or medical procedures that might be needed to maintain their health.

10.6 Clinical Study Termination

If the clinical study is prematurely terminated or suspended, the Sponsor will inform the Investigator and the regulatory authorities of the termination/suspension and the reasons thereof. The Investigator should promptly notify the IEC of the termination/suspension and of the reasons. The Sponsor reserves the right to close the investigational site or terminate the study in its entirety at any time, for any reasonable cause.

Reasons for the closure of an investigational site or termination of a study may include:

Successful completion of the study

The study's enrollment goals are met

The Investigator fails to comply with the protocol or GCP guidelines

Safety concerns

Sufficient data suggesting lack of effectiveness

Inadequate recruitment of subjects by the Investigator

The Investigator also may terminate the study at the investigational site for any reasonable cause. If the Sponsor terminates the study for safety reasons, it will immediately notify the Investigator by telephone and subsequently provide written confirmation of and instructions for study termination.

Print Date: Print Date:

Document: TDOC-0053541 **Version:** 3.0; Most-Recent; Effective; CURRENT

Status: Effective Page 44 of 59

11 ANALYSIS PLAN

Continuous variables will be summarized using the number of observations, mean, standard deviation (SD), median, minimum and maximum, as well as confidence intervals or confidence limits where applicable. Categorical variables will be summarized with counts and percentages from each category. Any deviations to this analysis plan will be updated during the course of the study as part of a protocol amendment or will be detailed in the clinical study report.

11.1 Subject Evaluability

The final subject evaluability will be determined prior to breaking the code for masked lens sequence assignment and locking the database, based upon the DEP.

11.2 Analysis Data Sets

11.2.1. Safety Analysis Set

Safety analyses will be conducted using the Safety Analysis Set on a treatment-emergent basis. The Safety Analysis Set will include all subjects/eyes exposed to any study lenses (AOHG or VITA) evaluated in this study. For treatment-emergent safety analyses, subjects/eyes will be categorized under the actual lens exposed.

11.2.2 Full Analysis Set

The FAS is the set of all randomized subjects who are exposed to any study lenses (AOHG or VITA) evaluated in this study.

11.2.3. Per Protocol Analysis Set

The PP Analysis Set is a subset of all randomized subjects and excludes all data/subjects that meet any of the critical deviation or non-evaluable criteria identified in the DEP.

11.3 Demographic and Baseline Characteristics

Demographic information (age and sex) will be summarized for the Safety, Fu	ll, and PP
Analysis Sets. Baseline characteristics on habitual lenses	and VA will
be summarized for the Full and the PP Analysis Sets.	

11.4 Effectiveness Analyses

This study defines 1 primary,	
endpoints. All effectiveness e	valuations will use the FAS as the primary analysis set.

Document: TDOC-0053541 **Version:** 3.0; Most-Recent; Effective; CURRENT

Status: Effective Page 45 of 59

Supportive analyses of the primary endounced endpoints will be conducted using the PP Analysis Set only if the number of subjects excluded from the PP analysis set exceeds 5% of the FAS.

For all planned inferential analyses, alternative models/methods may be considered if convergence cannot be achieved.

11.4.1. Primary Effectiveness Analysis

The primary objective of this study is to demonstrate superiority of AOHG compared with VITA in total lipid uptake (total of surface and bulk uptake) after 30 days of wear by high lipid depositors.

The corresponding endpoint is the total amount of lipids (µg) absorbed/adsorbed and extracted (total of surface and bulk uptake) from worn test and control lenses at Day 30. Only OD lenses will be used for the *ex vivo* analysis.

11.4.1.1. STATISTICAL HYPOTHESES

The null and alternative hypotheses are formulated as follows:

$$H_0: \mu_T - \mu_C \ge 0$$

$$H_a$$
: $\mu_T - \mu_C < 0$

where μ_T and μ_C represent the mean total lipid uptake (total of surface and bulk uptake) measured from the test and control lenses, respectively.

11.4.1.2. ANALYSIS METHODS

A mixed effect repeated measures model will be fit to test these hypotheses. To account for within-subject correlation due to crossover, the model will include terms for lens, period, and lens sequence group as fixed effects and subject as a random effect. Normality will be checked. If the normality assumption does not hold, a natural log transformation will be performed as $\log_e(\mu g+1)$.

11.4.2. Secondary Effectiveness Analysis

No secondary effectiveness objective is defined for this study.

Document: TDOC-0053541 **Version:** 3.0; Most-Recent; Effective; CURRENT

Status: Effective Page 46 of 59

Effective Date: 07-Dec-2017

[figure not shown]
Document: TDOC-0053541 **Version:** 3.0; Most-Recent; Effective; CURRENT

Status: Effective Page 47 of 59

Effective Date: 07-Dec-2017

Document: TDOC-0053541 **Version:** 3.0; Most-Recent; Effective; CURRENT

[figure not shown]
Status: Effective Page 48 of 59

11.5. Handling of Missing Data

All data obtained in evaluable subjects/eyes will be included in the analysis. No imputation for missing values will be carried out for the effectiveness analysis.

Page 49 of 59 Status: Effective

11.7. Safety Analysis

The safety endpoints for this study are Biomicroscopy Findings, AEs, and Device Deficiencies.

Descriptive summaries (counts and percentages) for ocular and nonocular AEs will be presented by Medical Dictionary for Regulatory Activities (MedDRA) Preferred Terms. In addition to an overall presentation of AEs, relationship to lens will be identified. Serious Adverse Events will also be tabulated separately. Individual subject listings will be provided, as necessary.

Additionally, individual subject listings will be provided for AEs that:

Occur after signing the Informed Consent Form, but prior to exposure to test or control lenses (pre-treatment)

Occur after last exposure to Period 1 lenses, but prior to exposure to Period 2 lenses (between-period)

Each Biomicroscopy parameter will be tabulated by its grade. Counts and percentages of eyes that experience an increase of ≥ 2 grades from Visit 3/Visit 5 to any subsequent visit within each period will be presented. A supportive listing will be generated which will include all Biomicroscopy data from the visits within each affected period for those eyes experiencing the increase of ≥ 2 grades, with the following variables: lens, Investigator, subject, age, sex, visit, eye, parameter, baseline value, and value at the visit.

Frequency counts will be tabulated for each Device Deficiency category. Additionally, 2 listings will be provided: prior to exposure to study lens and treatment-emergent.

No inferential testing will be done for the safety analysis.

Document: TDOC-0053541 **Version:** 3.0; Most-Recent; Effective; CURRENT

Status: Effective Page 50 of 59

11.8. Health Economics

Not applicable.

11.9. Interim Analyses

Not applicable.

11.10 Sample Size Justification

Sample sizes per sequence group required to attain 80% power at 1-sided, α =0.05 for the primary endpoints are shown below:

Endpoint	Assumptions	N/sequence group
Primary		
Ex vivo total lipid uptake (total of surface and bulk uptake)	SD paired differences = 13.88 Detectable difference = 10	7 (based upon t-test for difference of means in 2x2 crossover design)

Effective Date: 07-Dec-2017 Document: TDOC-0053541 Version: 3.0; Most-Recent; Effective; CURRENT

[figure not shown]
Status: Effective Page 51 of 59

12 ADVERSE EVENTS AND DEVICE DEFICIENCIES

12.1 General Information

An AE is any untoward medical occurrence, unintended disease or injury, or untoward clinical signs (including abnormal laboratory findings) in subjects, users, or other persons, whether or not related to the study lenses. For categories of AEs and SAEs, refer to the Glossary of Terms (see also Figure 12-1 and Figure 12-2).

Figure 12-1 **Categorization of all Adverse Events**

[figure not shown]

Document: TDOC-0053541 **Version:** 3.0; Most-Recent; Effective; CURRENT

Status: Effective Page 52 of 59

Effective Date: 07-Dec-2017

Figure 12-2 Categorization of all Serious Adverse Events

Document: TDOC-0053541 **Version:** 3.0; Most-Recent; Effective; CURRENT

Status: Effective Page 53 of 59

12.2 Monitoring for Adverse Events

At each visit, after the subject has had the opportunity to spontaneously mention any problems, the Investigator should inquire about AEs by asking the standard questions:

"Have you had any health problems since your last study visit?"

"Have there been any changes in the medicines you take since your last study visit?"

Changes in *any protocol-specific parameters and questionnaires (if applicable)* evaluated during the study are to be reviewed by the Investigator. Any untoward (unfavorable and unintended) change in *a protocol-specific parameter or questionnaire* response that is clinically relevant is to be reported as an AE. These clinically relevant changes will be reported regardless of causality.

12.3 Procedures for Recording and Reporting

AEs will be collected from the time of informed consent. Any pre-existing medical conditions or signs/symptoms present in a subject prior to the start of the study (ie, before informed consent is signed) will not be considered AEs in the study and should be recorded in the Medical History section of the eCRF.

In addition, temporary lens awareness or visual changes during the fitting process will not be considered AEs if the Investigator assesses that the symptom(s) can reasonably resolve within the anticipated adaptation period.

For each recorded event, the Adverse Device Effects (ADEs) and SAEs documentation must include: date of occurrence, severity, treatment (if applicable), outcome, and assessments of the seriousness and causality. In addition, the Investigator must document all Device Deficiencies reported or observed with test and control articles on the Device Deficiency eCRF. The investigational site must submit all available information on ADEs, SAEs, and Device Deficiencies to the Sponsor immediately as follows:

All SAEs must be reported immediately (within 24 hours) of the Investigator's or investigational site's awareness

Adverse device effects that do not meet the seriousness criteria, and Device Deficiencies must be reported within 10 calendar days of the Investigator's or investigational site's awareness

Document: TDOC-0053541 **Version:** 3.0; Most-Recent; Effective; CURRENT

Status: Effective Page 54 of 59

A printed copy of the completed *Serious Adverse Event and Adverse Device Effect* and/or *Device Deficiency* eCRF must be included with product returns (refer to CLL541-P001 Manual of Procedures for details on the return instructions)

Additional relevant information after initial reporting must be entered into the eCRF as soon as the data become available

Document any changes to concomitant medications on the appropriate eCRFs

Document all relevant information from Discharge Summary, Autopsy Report, Certificate of Death, etc, if applicable, in the narrative section of the Adverse Device Effect (for related AEs) and Serious Adverse Event eCRF

Note: Should the EDC system become non-operational, the investigational site must complete the appropriate paper Serious Adverse Event and Adverse Device Effect and/or Device Deficiency Form. The completed form is emailed to the Sponsor at [contact] according to the timelines outlined above; however, the reported information must be entered into the EDC system once it becomes operational.

Additionally, any AEs and Device Deficiencies for non-study marketed products (ie, contact lenses, with a processed as spontaneous (following the post-market vigilance procedures) and should be communicated to the product's manufacturer as per local requirements.

Sponsor representatives may be contacted for any protocol-related question and their contact information provided in the Manual of Procedures that accompanies this protocol.

Further, depending upon the nature of the AE or device deficiency being reported, the Sponsor may request copies of applicable portions of the subject's medical records. The Investigator must also report all AEs and Device Deficiencies that could have led to a Serious Adverse Device Effect (SADE) according to the requirements of regulatory authorities or IEC.

Document: TDOC-0053541 **Version:** 3.0; Most-Recent; Effective; CURRENT

Status: Effective Page 55 of 59

Intensity and Causality Assessments

Where appropriate, the Investigator must assess the intensity (severity) of the AE based upon medical judgment with consideration of any subjective symptom(s), as defined below:

Intensity (Severity)

Mild An AE is mild if the subject is aware of but can easily tolerate the sign or

symptom

Moderate An AE is moderate if the sign or symptom results in discomfort significant

enough to cause interference with the subject's usual activities

Severe An AE is severe if the sign or symptom is incapacitating and results in the

subject's inability to work or engage in their usual activities

For every AE in the study, the Investigator must assess the causality (Related or Not Related to the medical device or study procedure). An assessment of causality will also be performed by Sponsor utilizing the same definitions, as shown below:

Causality

Related An AE classified as related may be either definitely related or possibly related

where a direct cause and effect relationship with the medical device or study procedure has not been demonstrated, but there is a reasonable possibility that

the AE was caused by the medical device or study procedure.

Not Related An AE classified as not related may either be definitely unrelated or simply

unlikely to be related (ie, there are other more likely causes for the AE).

The Sponsor will assess the AEs and may upgrade the Investigator's assessment of seriousness and/or causality. The Sponsor will notify the Investigator of any AEs that is upgraded from non-serious to serious or from unrelated to related.

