Each safety variable will be summarized descriptively. AEs will be classified as pre-treatment, treatment-emergent, or between-period. Counts and percentages will be provided by relationship to lens, and separate tables will be generated for ocular and nonocular AEs. Counts and percentages in each grade category will be presented for each Biomicroscopy parameter. Device Deficiencies will also be tabulated. Supporting subject listings describing details of each safety variable will be provided. No inferential testing will be performed for the safety analysis.

Sample Size Calculation

Sample size calculation for the primary effectiveness endpoint (1-sided, α =0.05) is summarized below:

Primary Endpoint	Assumptions	Power	N/sequence group
Total lipid uptake (total of surface and bulk uptake)	SD paired differences = 13.88 Detectable difference = 10	80%	7

Document: TDOC-0053541 **Version:** 3.0; Most-Recent; Effective; CURRENT

Status: Effective Page 11 of 59

Effective Date: 07-Dec-2017

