3.2 Glossary of Terms

Adverse Event	Any untoward medical occurrence, unintended disease or injury, or untoward clinical signs (including abnormal laboratory findings) in subjects, users or other persons, whether or not related to the investigational medical device (test article). Note: For subjects, this definition includes events related to the test article, the control article, or the procedures involved. For users or other persons, this definition is restricted to events related to the test
Adverse Device Effect	article. Adverse event related to the use of an investigational medical device (test article) or control article. Note: This definition includes AEs resulting from insufficient or inadequate instructions for use, deployment, implantation, installation, or operation; any malfunction; and use error or intentional misuse of the test article or control article.
Device Deficiency	Inadequacy of a medical device with respect to its identity, quality, durability, reliability, safety, or performance. Note: This definition includes malfunctions, use errors, and inadequate labeling.
Malfunction	Failure of a medical device to meet its performance specifications or otherwise perform as intended. Performance specifications include all claims made in the labeling of the device. The intended performance of the device refers to the intended use for which the device is labeled or marketed.
Product Complaint	Any oral, electronic, or written communication that alleges deficiencies related to the identity (labeling), quality, durability, reliability, safety, effectiveness, or performance of a marketed product, including failure of the product, labeling or packaging to meet specifications, whether or not the product is related to or caused the alleged deficiency. A complaint may allege that an AE or medical device malfunction has occurred.
Non-Serious Adverse Event	Adverse event that does not meet the criteria for a serious adverse event.

Version: 3.0; Most-Recent; Effective; CURRENT Document: TDOC-0053541 Page 20 of 59 Status: Effective

Serious Adverse Event	Adverse event that led to any of the following: - Death
	- A serious deterioration in the health of the subject that either resulted in:
	a) A life-threatening illness or injury Note: Life-threatening means that the individual was at immediate risk of death from the event as it occurred, ie, it does not include an event which hypothetically might have caused death had it occurred in a more severe form.

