5.3.1 Adverse Events

The applicable definition of an Adverse Event (AE) is in the study protocol. All AEs occurring from when a subject signs informed consent to when a subject exits the study will be accounted for in the reporting.

Analysis and presentation of pre-treatment and between-treatment AEs will be separated from treatment-emergent AEs occurring during the study periods. A pre-treatment AE is an event that occurs after signing informed consent but prior to exposure to study lenses (AOHG or VITA). A between-treatment AE is an event that occurs after last exposure to Period 1 lenses but prior to exposure to Period 2 lenses. The period for treatment-emergent AE analysis starts from exposure to the study lenses for Period 1 or Period 2 until the subject completes or is discontinued from the study.

The following tables and supportive listings will be provided:

- Incidence of All Ocular Treatment-Emergent Adverse Events
- Incidence of All Nonocular Treatment-Emergent Adverse Events
- Incidence of Serious Ocular Treatment-Emergent Adverse Events
- Incidence of Serious Nonocular Treatmen-Emergent Adverse Events
- Listing of All Ocular Treatment-Emergent Adverse Events
- Listing of All Nonocular Treatment-Emergent Adverse Events
- Listing of All Ocular Pre-Treatment Adverse Events
- Listing of All Nonocular Pre-Treatment Adverse Events
- Listing of All Ocular Between-Treatment Adverse Events
- Listing of All Nonocular Between-Treatment Adverse Events

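### Causality is defined as one Related/Not Related judgement for lens or study procedure together, so the promised adverse event counts by relationship to lens are not secured

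*Protocol*

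**What the plan says.** **What is promised.** The Synopsis states: "Counts and percentages will be provided by relationship to lens, and separate tables will be generated for ocular and nonocular AEs". Section 11.7 repeats the commitment: "In addition to an overall presentation of AEs, relationship to lens will be identified". Both are specific to the lens.

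**What is collected.** Under the causality assessment in Section 12.3, the investigator "must assess the causality (Related or Not Related to the medical device or study procedure" for every AE. The definition of Related includes a reasonable possibility that "the AE was caused by the medical device or study procedure". The sponsor makes its own assessment using the same definitions.

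**How a device effect is defined.** The glossary (Section 3.2) gives an ADE as: "Adverse event related to the use of an investigational medical device (test article) or control article". Study procedures are not named there, although the AE entry just above it lists procedures as a possible cause distinct from the test and control articles. Section 12.3, in saying where supporting medical records are to be summarised, refers to the "Adverse Device Effect (for related AEs) and Serious Adverse Event eCRF".

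**What the SAP lists.** Section 5.3.1 has four incidence tables (all and serious events, ocular and nonocular), such as "Incidence of All Ocular Treatment-Emergent Adverse Events", and six listings. No title mentions relationship, and the section does not discuss causality.

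**The concern.** The promised summary needs a variable that says whether the lens caused the event. The only causality judgement that the protocol defines answers a wider question: whether the lens or a study procedure caused it. A combined answer cannot be split at analysis unless some other field holds the distinction.

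Collecting and describing AEs is the stated safety objective, and the results concern two marketed lenses from different manufacturers. In a descriptive safety analysis the counts are themselves the result. A figure labelled as lens-related that also holds procedure-only events would overstate what is attributed to the lens. The classification also matters for reporting, since Section 12.3 sets a 10-calendar-day limit for ADEs that are not serious.

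**Working it through.** The plan states no figure on this point, so there is none to reproduce. The check compares the texts, followed by an illustration of scale.

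**Step 1: compare the scope of each statement.**

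- Synopsis and Section 11.7 (output): lens only.
- Section 12.3 (causality judgement and definition of Related): lens or study procedure.
- Section 3.2 (ADE): test or control article only.
- Section 12.3 (label of the ADE form): related AEs, without saying related to what.
- SAP Section 5.3.1 (tables and listings): relationship not named.

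The output and the ADE definition have the same scope. The causality judgement is wider than both.

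**Step 2: follow a procedure-only event through the text.** Take an event at Visit 6 caused only by an examination at that visit. Section 10.2.6 places lens removal, biomicroscopy and refraction before study exit. SAP Section 5.3.1 runs the treatment-emergent window until the subject completes or discontinues, so the event is treatment-emergent. Under Section 12.3 it is Related. Under the glossary it is not an ADE. A summary by relationship built on the Section 12.3 answer would count it with the lens-related events.

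**Step 3: scale.** Let m be the number of subjects with a lens-related AE on a given lens, and k the number of further subjects whose only related AE on that lens was caused by a procedure. Take n = 78, the planned number randomized, and assume that all of them wear that lens. The values of m and k are assumptions.

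- Lens-related percentage = m/n
- Reported percentage = (m + k)/n
- Excess = k/n, whatever the value of m

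For k = 0, 1, 2, 3 the excess is 0/78 = 0, 1/78 = 1.3, 2/78 = 2.6 and 3/78 = 3.8 percentage points.

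With m = 3, the lens-related percentage is 3/78 = 3.8%. The reported percentage is 5/78 = 6.4% if k = 2 and 6/78 = 7.7% if k = 3. With m = 5 and k = 3, it is 8/78 = 10.3% against 5/78 = 6.4%.

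**The case against.** The strongest reply is that the wording in Section 12.3 says what must be assessed, not how many fields the form has. The eCRF and the Manual of Procedures are not among the documents, and Figure 12-1, which categorizes AEs, could not be consulted. Section 12.1 refers to the glossary for AE categories, and the glossary's ADE is confined to the device. Sections 9.3 and 12.4 also speak of product-related AEs. A lens-specific classification may therefore exist in practice. This stands, and it makes the point conditional on recording as worded. It does not remove the point: no text asks for two answers, and the one definition of Related accepts either cause.

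Second, the reference to the ADE form concerns where to write up supporting records and does not redefine an ADE. That is correct. It is loose wording to be aligned, not proof that procedure-only events become ADEs.

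Third, such events should be few. The ADE definition already takes in inadequate instructions and use error, so many lens-handling events belong there properly. Both periods have matching visits and the sequences are allocated 1:1, so there is little reason to expect a distorted comparison between lenses. This is fair; the issue is mainly the level of each count.

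Fourth, a reader might infer from SAP Section 5.3.1 that no lens-related counts will be produced. The documents do not support that. The commitment in Section 11.7 still stands, Section 11 requires deviations from it to be handled by amendment or disclosed in the study report, and the SAP gives only titles. A breakdown by relationship could sit inside a listed table. The omission is missing detail.

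**Conclusion.** The point holds in a limited form. The protocol defines one causality judgement covering lens or procedure, but promises counts by lens alone and defines an ADE by lens alone. Recorded as worded, procedure-only events would be classed as Related and could not be separated from lens-related events in the promised summary.

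The size is unknown. The range of 0 to 3.8 points rests on an assumed 0 to 3 procedure-only events among 78 subjects; with none, the error is zero. A reader might conclude that the lens-related or ADE counts will be too high. The documents do not establish this, since it needs both a single combined field and at least one procedure-only event.

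The consequence is confined to descriptive safety. Section 11.7 plans no inferential safety testing, and the primary endpoint and the success criterion are untouched. The change is worth making because it is cheap and because a combined answer cannot be separated later.

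**What to change.** 1. In Section 12.3 and the eCRF, record two answers for each AE: related to the study lens (yes/no) and related to a study procedure (yes/no). Use the same two answers for the sponsor's assessment. If the eCRF already does this, only the protocol text needs to change.
2. Let only the lens answer define an ADE and feed the summary by relationship to lens.
3. Reword the description of the ADE form in Section 12.3 so that it matches the glossary, for example by referring to lens-related AEs.
4. As a consistency edit, name in SAP Section 5.3.1 the summary of lens-related treatment-emergent AEs, ocular and nonocular, that the protocol already promises. SAP Section 2.1 already provides for analysis by the lens actually worn.

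The cost is one extra eCRF field and short text edits. The related count may fall slightly. No subjects or visits are added.
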